### 10.2 Key Secondary Efficacy Endpoint(s) and Analysis

Not applicable.

### 10.3 Other Secondary Efficacy Endpoint(s) and Analysis

The secondary analyses will be carried out using the analysis populations of FAS, PP1, and/or PP2.

Secondary variables are:

- The percentage of subjects with serum phosphorus levels at or below the age-specific KDOQI targets following 8 weeks of treatment with calcium carbonate followed by 8 weeks of treatment with lanthanum carbonate will be descriptively summarized similarly as for the primary efficacy variable, however, this will be performed for each treatment arm. The PP1 and FAS will be used for this summarization. (Table 3.1.2.1 and Table 3.1.2.2) The KDOQI serum phosphorus targets are defined above.

- Changes from baseline in serum phosphorus, calcium and calcium-phosphorus product in hyperphosphatemic children and adolescents with CKD who are on dialysis, following treatment with lanthanum carbonate for 8 weeks. The PP2 and FAS will be used for this summarization (**Table 3.1.4.1 to Table 3.1.4.6**) [Part 2 and 3 combined].
- Changes from baseline in serum phosphorus, calcium and calcium-phosphorus product in hyperphosphatemic children and adolescents with CKD who are on dialysis, following treatment with calcium carbonate for 8 weeks and lanthanum carbonate for 8 weeks. The PP1 and FAS Set will be used for this summarization (**Table 3.1.3.1 to Table 3.1.3.6**) [Part 2].
- Change from baseline in serum phosphorus, calcium and calcium-phosphorus product levels at the last visit of 8-week treatment period during Part 2 and monthly during the 6-month extension phase (Part 3). The PP2 and FAS Sets will be used for this summarization (**Table 3.1.4.1 to Table 3.1.4.6**) [Part 2 and 3 combined].
- Biochemical bone markers: bone ALP, osteocalcin, TRAP, FGF-23, PTH, sclerostin and fetuin-A before and after each treatment period in Part 2, and at the end of Part 3 (**Tables 3.1.5.1 to 3.1.5.14** [Part 2a and 3], **Tables 3.2.5.1 to 3.2.5.14** [Part 2b and 3]) will be summarized for PP1 and FAS and PP2 and FAS, respectively.
- Height and Weight at:
  - Visits 2.0, 2.4, 2.8, and 3.5 (Parts 2a and 3): (PP1 and FAS Sets)
  - Visits 1.0, 2.4, and 3.5 (Parts 2b and 3). (PP2 and FAS Sets)(**Tables 3.1.6.1 to 3.1.6.4, Tables 3.1.7.1 to 3.1.7.4**, respectively).
- Number and percentage of subjects with serum phosphorus levels at the age-specific KDOQI targets by week of treatment with lanthanum carbonate for PP2 and FAS (**Tables 3.1.8.1 to 3.1.8.2**, respectively).

All secondary variables will be summarised using descriptive statistics as follows:

- For continuous data: number of observations, mean, standard deviation, standard error, median, minimum, maximum values and 95% confidence interval (normal approximation) of the mean.
- For categorical data: number of observations and percentages.

All secondary efficacy endpoints will be summarised using both an appropriate PP Set (for the endpoint) and the FAS. Serum phosphorus, calcium, and calcium-phosphorus product will be summarized for Part 2 by treatment and weeks of administration of treatment, and for Part 2 and 3 combined for lanthanum carbonate only by weeks of treatment with lanthanum carbonate. For summaries by week of treatment, +/-1 week will be used to assign values to a timepoint ie, Week 8 will include 7-9 weeks of exposure. If more than 1 value for a subject falls into one window, then the value closest to the planned visit will be included in the summary, ie, if we have a value on day 51 and a value on day 57, the day 57 value will be used in the Week 8 summary. If two values are equidistance from the timepoint then the higher value will be used for analysis, assuming worst case.

All other secondary endpoints will be summarized by scheduled assessment.

It is stated in the protocol that local laboratory assessments for phosphorus, serum calcium, and calcium phosphorus product in Parts 1 and 2 are for titration purposes, as required, and will not be analyzed; data from Visits 3.0-3.4 will be collected and analysed. However, it should be clarified that in the case of missing central laboratory data, local laboratory data will be used, as appropriate. For example, in the case of the change from baseline to an assessment following 8 weeks of an IP, both assessments (baseline and following 8 weeks of treatment) must be from either the central or the local lab.

Bar charts will be provided for the mean change from baseline in Part 2 by treatment group for serum phosphorus, **(Figure 3.1.3.1)** calcium **(Figure 3.1.3.2,)**, and calcium-phosphorus product **(Figure 3.1.3.3)** for the PP1 Set.

The mean change from baseline in Part 2 and 3 combined by weeks of treatment with lanthanum carbonate will also be graphically presented, via line graph for serum phosphorus, calcium, and calcium-phosphorus product for the following Analysis Populations: PP2, FAS Sets. **(Figures 3.1.4.1 to 3.1.4.6)**

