**Table 3: Schedule of Assessments for Part 2b and Part 3**

	Part 2b (Visit window $\pm 3$ days)				Part 3 (Visit window $\pm 1$ week)		
Visit	1.0 a	Washout W1 b	2.1-2.3	2.4	3.0-3.4	3.5/End of Study c	Safety Follow-up call j
Week	0	0-3 weeks duration	2, 4, 6 d	8 d	12, 16, 20, 24, 28	32 d	33-34 d
Pregnancy test (where applicable)	✓					✓	
Lanthanum pharmacokinetics			✓ f		✓ g		
Investigational product dispensed	✓ h	✓ h	✓	✓ i	✓		
Investigational product collected			✓	✓	✓	✓	
Dose adjustment (as needed) and compliance			✓	✓	✓	✓	
Record adverse events	✓	✓	✓	✓	✓	✓	✓
Record concomitant medication	✓	✓	✓	✓	✓	✓	✓
Dialysis adequacy	✓		✓	✓	✓	✓	
Confirmation of dietary advice	✓		✓	✓	✓	✓	

a A consent form to participate in Part 2b must be signed.

b Only for subjects completing washout.

c Assessments scheduled for Visit 3.5 should also be carried out at the time of discontinuation for all subjects who withdraw from the study early or as close as possible to the time of discontinuation. These assessments are not required for subjects post-transplantation; however a safety follow-up call is required.

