#### 4.4.1 Subject Stopping Criteria

Subjects must be removed from study if any 1 or more of the following events occur:

- Violation of inclusion/exclusion criteria at study entry
- Taking another non-study phosphate binder (on either calcium carbonate and lanthanum carbonate arms) rather than the investigational product during the study
- Kidney transplant during the study. Subjects should be followed 30±7 days post-transplant
- Pregnancy
- Serum phosphorus rises above 10.0mg/dL (3.23mmol/L) during the study (however this does not apply during the washout periods)
- Calcium level rises to >11.5mg/dL (2.88mmol/L) during the first treatment period of Part 2a (calcium carbonate). Subjects may continue to Part 3 but must complete all procedures for Visit 2.4 prior to commencing Part 3.

See [APPENDIX 2](#) for guidelines on phosphorus and calcium levels.

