#### 4.4.2 Reasons for Discontinuation

The reason for withdrawal must be determined by the Investigator and recorded in the subject's medical record and on the CRF. If a subject is withdrawn for more than 1 reason, each reason should be documented in the source document and the most clinically relevant reason should be entered on the CRF.

If an adverse event (AE) is a reason for discontinuation, then "adverse event" must be recorded as the reason for discontinuation on the CRF.

Reasons for discontinuation include but are not limited to:

- Death
- Withdrawal by subject
- Lost to follow-up
- Lack of efficacy
- Physician decision
- Pregnancy
- Kidney transplant
- Other (must be specified. eg, met stopping 1 or more stopping criteria).

Reasons for possible discontinuation (to be determined by Sponsor and Investigator discussion) include but are not limited to:

- Adverse event
- Protocol violation
- Non-compliance with study drug
- Progressive disease.

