#### **3.1.2 Secondary Objectives**

1. To investigate the safety profile in hyperphosphatemic children and adolescents with CKD on dialysis treated with calcium carbonate and/or lanthanum carbonate.
2. To summarize the percentage of subjects achieving KDOQI targets for serum phosphorus in hyperphosphatemic children and adolescents with CKD who are on dialysis following treatment with calcium carbonate for 8 weeks and lanthanum carbonate for 8 weeks.
3. To assess mean changes from baseline in serum phosphorus, calcium and calcium-phosphorus product in hyperphosphatemic children and adolescents with CKD who are on dialysis, following treatment with lanthanum carbonate for 8 weeks.
4. To summarize mean changes from baseline in serum phosphorus, calcium and calcium-phosphorus product in hyperphosphatemic children and adolescents with CKD who are on dialysis, following treatment with calcium carbonate for 8 weeks and lanthanum carbonate for 8 weeks.
5. To describe the pharmacokinetics (maximum plasma concentration [Cmax] and area under the plasma concentration-time curve from time zero to the time of the last quantifiable concentration [AUC0-t; body weight-normalized) of lanthanum carbonate in hyperphosphatemic children and adolescents aged 10 years to <18 years with CKD who are on dialysis, after a single dose of lanthanum carbonate oral powder formulation is administered (Part 1 of the study).
6. To investigate the efficacy (serum phosphorus, calcium, and calcium phosphorus product) and safety of up to 8 months of treatment with lanthanum carbonate in children and adolescents aged 10 years to <18 years (Parts 2 and 3 of the study combined).
7. To investigate biochemical markers of bone metabolism including bone alkaline phosphatase (ALP), tartrate-resistant acid phosphatase (TRAP), osteocalcin, fibroblast growth factor 23 (FGF-23), parathyroid hormone (PTH), sclerostin and fetuin-A in children and adolescents aged 10 years to <18 years with CKD who are on dialysis.
8. To investigate growth in children and adolescents aged 10 years to <18 years with CKD who are on dialysis and weight.

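### The ±1-week windows in SAP 10.3 leave 46% of Part 3 days unassigned, so an early-termination value or a drifted visit can fall out of the long-term by-week efficacy tables

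*SAP*

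**What the plan says.** SAP 10.3 defines the assignment rule: "For summaries by week of treatment, +/-1 week will be used to assign values to a timepoint ie, Week 8 will include 7-9 weeks". When several values from one child share a window, only the one nearest the target is kept, and the higher is used if two are equally distant.

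The rule governs two sets of long-term efficacy outputs. One is change from baseline in phosphorus, calcium and their product, reported at the end of the 8-week period and then "monthly during the 6-month extension phase (Part 3"), in Tables and Figures 3.1.4.1-3.1.4.6. The other is "Number and percentage of subjects with serum phosphorus levels at the age-specific KDOQI targets by week of treatment with lanthanum carbonate", in Tables 3.1.8.1-3.1.8.2. Both serve secondary objective 6 (SAP 3.1.2), which covers efficacy and "safety of up to 8 months of treatment with lanthanum carbonate".

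Protocol Table 3 puts the Part 3 visits at Weeks 12, 16, 20, 24, 28 and 32, each with a visit window of ±1 week. Footnote c adds: "Assessments scheduled for Visit 3.5 should also be carried out at the time of discontinuation for all subjects who withdraw from the study early". The Visit 3.5 panel includes biochemistry, which contains phosphorus and calcium. It is not required after a transplant.

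The SAP does not say what happens to a by-week efficacy value that lies outside every window.

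**The concern.** A half-width of one week suits visits every 2 weeks, because neighbouring windows then meet. Applied to visits every 4 weeks, it leaves a hole of nearly two weeks between each pair of timepoints. Scheduled visits that keep to time are safe. The exposed values are those not tied to the grid: the panel taken at discontinuation, and visits that slip relative to the first lanthanum dose.

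Exit values are informative because some reasons for leaving are themselves the outcome. Protocol 4.4.1 requires removal if "Serum phosphorus rises above 10.0mg/dL (3.23mmol/L) during the study" (washout excepted), and Protocol 4.4.2 lists "Lack of efficacy" as a reason for discontinuation. If such a child's last value lands in a gap, the by-week tables omit a measurement that was collected and that bears on objective 6. With no rule in the SAP, the handling would be settled at programming, in an open-label study.

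**Working it through.** **Inputs.** Half-width 7 days (SAP 10.3). Lanthanum timepoints at Weeks 2, 4, 6 and 8 in Part 2 and Weeks 12, 16, 20, 24, 28 and 32 in Part 3 (Protocol Table 3). For Part 2a, nominal study Weeks 20 to 40 less the 8 calcium carbonate weeks give the same lanthanum weeks. Target day = 7 × week; a day is covered if |day − target| ≤ 7. The grid is inferred from the schedule, because the table shells are a separate document.

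**The plan's own example.** Week 8: 56 ± 7 = days 49-63, which is 7-9 weeks as stated. Days 51 and 57 are both inside, and 57 is closer (1 day against 5), as the SAP says.

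**Part 2.** Days 7-56: 0 of 50 uncovered.

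**Part 3.** For targets 28 days apart, one window ends at T + 7 and the next begins at T + 21, so T + 8 to T + 20 is uncovered: 13 days. The gaps are days 64-76, 92-104, 120-132, 148-160, 176-188 and 204-216. Total 6 × 13 = 78 of 168 days (57-224), or 46.4%.

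**Sensitivity to the grid.** For a child going straight from calcium carbonate to Part 3, over days 1-168 of lanthanum, 58 days (34.5%) are uncovered if Weeks 2 and 6 are on the grid, and 50.6% if it is monthly only. A 2-weekly grid in the shells would leave 0%.

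**Values affected.** Exit numbers are not given, so a range is shown, assuming exit times uniform over Part 3. Expected values in a gap = k × 78/168:

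| Early-termination samples, k | Expected in a gap |
|---|---|
| 5 | 2.3 |
| 10 | 4.6 |
| 15 | 7.0 |
| 20 | 9.3 |

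If 30% to 50% of 10 discontinuations were transplants without a sample (assumption), the expectation falls to 0.7 × 4.6 = 3.2 or 0.5 × 4.6 = 2.3.

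**What wider windows would recover.** Suppose visits fall exactly on target days. An exit value is tabulated only if it is in a window and no scheduled value there is closer to the target.

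- Now: the 8 days from T − 7 to T in each of six windows, 6 × 8 = 48 of 168 days. Another 78 days are in gaps. The remaining 42 are inside a window but displaced by the scheduled value (48 + 78 + 42 = 168).
- With contiguous windows (Week 12 = days 64-98, Week 16 = days 99-126, then 28 days each): 21 days for Week 12 plus 14 for each of five later weeks, 21 + 70 = 91 of 168. No day is uncovered, but 77 remain displaced.

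Contiguous windows therefore help, but they are only part of the remedy.

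**The case against.** The strongest reply is that little is lost. The Part 3 visit window equals the analysis window, so on-schedule monthly values are captured, and SAP 10.3 confirms that local results from Visits 3.0-3.4 are analysed. A phosphorus above 10.0 mg/dL found at such a visit is in the table. Outcome-driven exits should cluster near visits, so uniform timing is least plausible for the children who matter most, and transplant leavers need no sample. The SAP is silent rather than instructing anyone to discard, and unseen shells might hold a finer grid. Phosphorus and calcium also appear in the by-visit safety laboratory tables (SAP 11.2), with no ±1-week rule, and in Listings 6.1 and 8.1.2. Withdrawals are tabulated by reason (SAP 5).

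Most of this stands, and it limits the size of the point. It does not close the gap in the efficacy tables. The safety tables specify no percentage at KDOQI target and no summary by lanthanum week. The last-value convention in SAP 18.3 is confined to safety parameters. Disposition is not shown by week.

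A reader might infer that the windows make the long-term result describe only children who stayed. The documents do not support that. Observed-case rows hold only children with data at that week whatever the window width, leavers' earlier values remain in the Full Analysis Set, and some exit values do fall in a window. Nor does 46% of days mean 46% of exit values lost: that needs uniform exit times, which nothing in the documents establishes.

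**Conclusion.** The point holds as a limited defect in the secondary, descriptive long-term analysis. On the monthly grid implied by the protocol, 78 of 168 Part 3 days (46%) have no timepoint, and the SAP gives no rule for an efficacy value that falls there. The day count depends only on that inferred grid. The number of values affected cannot be stated, and the table above is conditional on assumed exit counts and uniform timing.

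The gaps add to attrition bias in the late-week rows but are not its main source, and the documents give no Part 3 dropout figures from which to size that bias. The Week 8 primary endpoint is unaffected, and the omitted values are still reported elsewhere. The change is worth making because it is cheap and uses data already collected.

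**What to change.** 1. Add to Tables 3.1.4.1-3.1.4.6 and 3.1.8.1-3.1.8.2 a row for the last on-treatment value on lanthanum, with every lanthanum-treated subject of the analysis set as the fixed denominator. Define on-treatment for this row, since the exit panel may be drawn shortly after dosing stops, and show how many subjects have no such value. Read this row beside Week 32 when answering objective 6. A version counting removals for phosphorus above 10.0 mg/dL or lack of efficacy as not at target can be added as a labelled sensitivity analysis; it answers a different question.
2. State the Part 3 timepoint grid in SAP 10.3 and make its windows contiguous: keep Week 8 at days 49-63, then Week 12 = days 64-98, Week 16 = days 99-126, and 28-day windows to Week 32. This assigns values now in a gap. It does not recover an exit value taken after a scheduled visit in the same window, which is why item 1 is needed.
3. Show the number observed and the number withdrawn at each week.

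The cost is SAP wording, one row per table and two counts per week, with no new data. The downside is that Part 3 rows become less homogeneous in exposure time, most of all Week 12, which would take in values from just after Week 9.

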#### **10.4 Exploratory Efficacy Endpoint(s) and Analyses**

Not applicable.

## 11. SAFETY ANALYSES

For scheduled assessment all safety variables for Part 1 will be summarised using the Safety Analysis Set 1; Safety variables for Parts 2 and 3 will be summarised using the Safety Analysis Set 2 and SCS (where applicable). Safety variables include AEs, clinical laboratory variables, vital signs, and electrocardiogram (ECG) variables. For each safety variable, the last value collected before the first dose of IP will be used as baseline for all analyses of that safety variable. Additionally, a detailed description of Baseline, for treatment groups in Parts 2 and 3, can be found in the TLG shells, Appendix 2.

### 11.1 Adverse Events

Onset day of an AE is calculated as (start date of the AE - date of the first dose of IP) + 1. AEs will be classified into system organ class (SOC) and preferred term (PT) using Version 16.1, of MedDRA, to be determined closer to the conclusion of data collection.

An AE that occurs during the study will be considered a treatment emergent AE (TEAE) if it has a start date on or after the first dose of IP. TEAEs will be allocated to Part 1, Part 2, or Part 3, based on the onset date of the AE relative to the date and Part of the most recently administered IP. If an AE occurred more than 3 weeks after the date of the most recent IP, it will not be considered a TEAE. In the case of increases in severity, if there is more than 1 reference AE with the same preferred term then the AE with the greatest severity will be used as the benchmark for comparison to the AEs occurring in each Part of the study.

**Part 1:** An overall summary (**Table 4.2.1.1**) and summary by age group (**Table 4.2.1.2**) of the number of subjects in Safety Analysis Set 1 with TEAEs in Part 1 will be presented, including the number and proportion of subjects with any TEAEs, serious TEAEs, TEAEs related to lanthanum carbonate, TEAEs leading to study withdrawal, and TEAEs leading to death. The number of events, incidence, and percentage of TEAEs will be presented by SOC, and by preferred term (**Table 4.2.2.1**); by SOC, preferred term, and maximum severity (**Table 4.3.1.1**); and by SOC, preferred term, and relationship to lanthanum carbonate (**Table 4.3.2.1**). Similar summaries by SOC and preferred term will be produced for SAEs (**Table 4.4.1.1**), for deaths (**Table 4.4.2.1**), and for TEAEs leading to study withdrawal (**Table 4.4.3.1**). AEs (**Listing 7.1**), SAEs (**Listing 7.2**), AEs related to lanthanum carbonate (**Listing 7.3**), AEs leading to study withdrawal (**Listing 7.4**), and deaths (**Listing 7.5**) will be listed. AEs related to bone disease (preferred terms: adynamic bone disease and long bone fracture) are of special interest and will be summarised by SOC and preferred term (**Tables 4.5.1.1 and 4.5.2.1**) and listed separately (**Listing 7.6**).

**Part 2:** An overall summary (**Table 4.2.1.3**) and summary by age group (**Table 4.2.1.4**) of the number of subjects in Safety Analysis Set 2 with TEAEs in Part 2 will be presented, including the number and proportion of subjects with any TEAEs, serious TEAEs, TEAEs related to IP, TEAEs leading to study withdrawal, and TEAEs leading to death. The number of events, incidence, and percentage of TEAEs in each treatment group will be presented by SOC and preferred term (**Table 4.2.2.2**); by SOC, preferred term, and maximum severity (**Table 4.3.1.2**); and by SOC, preferred term, and relationship to IP (**Table 4.3.2.2**). Similar summaries by SOC and preferred term will be produced for SAEs (**Table 4.4.1.2**), for deaths (**Table 4.4.2.2**), and for

TEAEs leading to study withdrawal (**Table 4.4.3.2**). AEs, AEs related to IP, SAEs, AEs leading to study withdrawal, and deaths will be listed (**Listing 7.1, Listing 7.3, Listing 7.4 and Listing 7.5**). TEAEs related to bone disease (preferred terms: adynamic bone disease and long bone fracture) are of special interest and will be summarised by SOC and preferred term for Part 2 (**Tables 4.5.1.2 and 4.5.2.2**) and listed separately (**Listing 7.6**).

**Part 2 and 3 combined (lanthanum carbonate only):** An overall summary (**Tables 4.2.1.5 and 4.2.1.7**) and summary by age group (**Tables 4.2.1.6 and 4.2.1.8**) of the number of subjects in Safety Analysis Set 2 and SCS with TEAEs in Part 2 and 3 combined will be presented. The number of events, incidence, and percentage of TEAEs will be presented by SOC by preferred term (**Tables 4.2.2.3 and 4.2.2.4**); by SOC, preferred term, and maximum severity (**Tables 4.3.1.3 and 4.3.1.4**); and by SOC, preferred term, and relationship to lanthanum carbonate (**Tables 4.3.2.3 and 4.3.2.4**). Similar summaries by SOC and preferred term will be produced for SAEs (**Tables 4.4.1.3 and 4.4.1.4**), for deaths (**Tables 4.4.2.3 and 4.4.2.4**), and for TEAEs leading to study withdrawal (**Tables 4.4.3.3 and 4.4.3.4**). AEs, AEs related to lanthanum carbonate, SAEs, AEs leading to study withdrawal, and deaths will be listed (refer to listings noted above). TEAEs related to bone disease (preferred terms: adynamic bone disease and long bone fracture) are of special interest and will be presented by SOC and preferred term in **Table 4.5.1.3 and Table 4.5.1.4** and by sex and age group in **Table 4.5.2.3 and 4.5.2.4** and will be listed separately. (**Listing 7.6**)

Only Part 2 will be summarised by treatment group (Calcium Carbonate and Lanthanum Carbonate) for the Safety Analysis Set 2 population summary.

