## 1. BACKGROUND INFORMATION

### 1.1 Condition Background and Current Treatment

#### Chronic kidney disease

Lanthanum carbonate has been developed as a phosphate-binding agent for the treatment of hyperphosphatemia associated with chronic kidney disease (CKD). Control of serum phosphate levels is fundamental in the management of CKD, which leads to progressive decline in the kidney's ability to excrete phosphate, produce active vitamin D (calcitriol), and maintain calcium homeostasis.

CKD is associated with complex metabolic, bone and vasculature abnormalities that together encompass a syndrome defined in 2006 as CKD-mineral and bone disorder ([Moe et al. 2006](#)). Hyperphosphatemia and secondary hyperparathyroidism are implicated as central components in CKD- mineral and bone disorder.

The pathophysiological consequences of positive phosphate balance and hyperphosphatemia include hyperparathyroidism and the associated renal osteodystrophy. Hyperphosphatemia and hyperparathyroidism in CKD is a vicious cycle with serious consequences. The associated high turnover bone disease manifests with bone pain, bone fracture, bone deformity, osteopenia, myopathy, arthritis, resistance to erythropoietin due to marrow fibrosis, growth failure in children, and extraskeletal calcification.

Serum phosphorus levels vary depending on age ([Kidney Disease Outcomes Quality Initiative \[KDOQI\] Guideline 4, 2005](#)).

A limited number of clinical studies have been conducted in the pediatric population with phosphate binders ([Pieper et al. 2006](#); [Alon et al. 1986](#); [Clark et al. 1989](#); [Mahdavi et al. 2003](#); [Salusky et al. 2005](#)). Currently the only such products with an approved indication in children are calcium-based binders and aluminium hydroxide.

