### 2.2.2 Secondary Objectives

1. To investigate the safety profile in hyperphosphatemic children and adolescents with CKD on dialysis treated with calcium carbonate and/or lanthanum carbonate.
2. To summarize the percentage of subjects achieving KDOQI targets for serum phosphorus in hyperphosphatemic children and adolescents with CKD who are on dialysis following treatment with calcium carbonate for 8 weeks and lanthanum carbonate for 8 weeks.
3. To assess mean changes from baseline in serum phosphorus, calcium and calcium-phosphorus product in hyperphosphatemic children and adolescents with CKD who are on dialysis, following treatment with lanthanum carbonate for 8 weeks.
4. To summarize mean changes from baseline in serum phosphorus, calcium and calcium-phosphorus product in hyperphosphatemic children and adolescents with CKD who are on dialysis, following treatment with calcium carbonate for 8 weeks and lanthanum carbonate for 8 weeks.
5. To describe the pharmacokinetics (maximum plasma concentration [ $C_{max}$ ] and area under the plasma concentration-time curve from time zero to the time of the last quantifiable concentration [ $AUC_{0-t}$ ]; body-weight-normalized) of lanthanum carbonate in hyperphosphatemic children and adolescents aged 10 years to <18 years with CKD who are on dialysis, after a single dose of lanthanum carbonate oral powder formulation is administered (Part 1 of the study).
6. To investigate the efficacy (serum phosphorus, calcium, and calcium-phosphorus product) and safety of up to 8 months of treatment with lanthanum carbonate in children and adolescents aged 10 years to <18 years (Parts 2 and 3 of the study combined).
7. To investigate biochemical markers of bone metabolism including bone alkaline phosphatase (ALP), tartrate-resistant acid phosphatase (TRAP), osteocalcin, fibroblast growth factor 23 (FGF-23), parathyroid hormone (PTH), sclerostin and fetuin-A in children and adolescents aged 10 years to <18 years with CKD who are on dialysis.

8. To investigate growth in children and adolescents aged 10 years to <18 years with CKD who are on dialysis.

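### The bone events of special interest count only one exact fracture term, so fractures coded to any other term drop out of the Bone Disease tables and listing

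*SAP*

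**What the plan says.** SAP 11.1 sets up one category of adverse events of special interest, bone disease, and defines it in a parenthesis. For Part 1: "AEs related to bone disease (preferred terms: adynamic bone disease and long bone fracture) are of special interest". For Part 2, and again for Parts 2 and 3 combined on lanthanum carbonate: "TEAEs related to bone disease (preferred terms: adynamic bone disease and long bone fracture) are of special interest". Nothing marks the two terms as examples, and no grouped query or wider term list is cited.

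The category feeds three sets of outputs, named in SAP 20:

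- Tables 4.5.1.1 to 4.5.1.4, by system organ class and preferred term, with Part 2 split by treatment group.
- Tables 4.5.2.1 to 4.5.2.4, by sex and age group.
- Listing 7.6.

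Their titles speak of bone disease events and do not mention the two-term limit.

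Protocol 1.1 describes the bone disease of this population more broadly: "The associated high turnover bone disease manifests with bone pain, bone fracture, bone deformity, osteopenia", and goes on to other manifestations. Protocol 9.11 defines no special-interest events.

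All treatment-emergent events are also reported in general tables. For Part 2: "The number of events, incidence, and percentage of TEAEs in each treatment group will be presented by SOC and preferred term". Every adverse event is in Listing 7.1.

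**The concern.** The SAP has already decided that fracture belongs among the bone events worth separate attention, but it admits only one fracture term. A fracture coded to another term would be missing from a table whose title suggests that it covers bone disease events generally. A zero or a very low count could then reflect the term list and not the patients.

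This matters more here than in most trials of this size. Amendment 5 moved the focus of the study to safety (Protocol 9.13), bone disease is the only adverse event category that the SAP singles out, and bone metabolism is a secondary objective (Protocol 2.2.2: "To investigate biochemical markers of bone metabolism including bone alkaline phosphatase (ALP"). With so few subjects, one affected child more or less changes what the table appears to say.

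**Working it through.** **Step 1: set the texts side by side.**

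| Item | Protocol 1.1 | SAP 11.1 group |
|---|---|---|
| Fracture | Bone fracture, no limit of site | The preferred term long bone fracture only |
| Adynamic bone disease | Not in the list of manifestations | Included |

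The SAP selects by preferred term, so inclusion depends on the coded term and not on what the investigator wrote. A fracture enters the outputs only if it is coded to that one term.

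**Step 2: can the coding be predicted from the documents?** No. SAP 11.1 names MedDRA 16.1 but leaves the choice until nearer the end of data collection, while Protocol 9.11 names version 13.0. Neither document says which term a fracture at a named site would receive. The gap in the rule is certain; the number of events that fall through it is not.

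**Step 3: what is lost and what is kept for such a fracture?**

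- Kept: its row in the general tables by system organ class and preferred term, its place in the severity and relationship tables, any entry as a serious event or a withdrawal, and Listing 7.1.
- Lost: its place in a single count of subjects with a bone event (4.5.1.x), the treatment-group split of that count in Part 2 (4.5.1.2), the sex and age breakdown (4.5.2.x), and Listing 7.6.

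**Step 4: scale, by illustration.** The only detection figures in the plan are for at least one event at a true rate of 5%:

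- SAP 2.5, n = 32: 1 − 0.95^32 = 80.6%, as stated.
- Protocol 9.13, n = 35: 1 − 0.95^35 = 83.4%, as stated.

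Now assume, for illustration only, that 5% of subjects have adynamic bone disease or any fracture, and that a share f of those subjects have an event coded to one of the two terms. The documents give neither figure. The chance that the special-interest table shows at least one subject is 1 − (1 − 0.05f)^n:

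| f | n = 32 | n = 35 | n = 65 |
|---|---|---|---|
| 1 | 80.6% | 83.4% | 96.4% |
| 0.75 | 70.6% | 73.8% | 91.7% |
| 0.5 | 55.5% | 58.8% | 80.7% |
| 0.25 | 33.1% | 35.6% | 55.9% |
| 0.1 | 14.8% | 16.1% | 27.8% |

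The n = 65 column uses the approximate maximum enrolment, as if all took lanthanum carbonate. At n = 32 the expected number of affected subjects is 32 × 0.05 = 1.6. If half are captured it is 0.8, so the choice of terms can by itself decide whether the table is empty.

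**The case against.** The best reply is that Protocol 1.1 is disease background and not a search list. It describes high turnover disease, whereas the SAP group includes adynamic bone disease, which is not in that list, so the group was evidently not drawn from it. Since the protocol defines no special-interest events, the SAP adds to it and breaches nothing. Every event is tabulated elsewhere, in a trial small enough for the general tables to be read line by line. Bone is also followed through seven markers, and growth through height. The preferred-term rows in Tables 4.5.1.x show which terms were counted, and the table shells, a separate document, may carry a footnote. No decision rule uses the count.

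Most of this stands, and it sets the size of the point. It also disposes of a stronger reading. A reader might infer that the SAP wrongly leaves out bone pain, bone deformity and osteopenia as well, and count how many of the named manifestations are missing. The documents do not support that as an error. Protocol 8.1.4 keeps symptoms of the disease out of adverse event recording while they stay within expected progression, so adding these terms would mix underlying disease with the safety signal and would depend on each investigator's view of worsening. A count of absent list entries also says nothing about events missed.

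The reply does not remove the fracture point. The SAP itself treats a fracture as an event of special interest; it gives no reason for stopping at one term, and the output titles do not show that it did.

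**Conclusion.** The point holds for fractures. The bone group is closed at two exact preferred terms, so any fracture coded otherwise is left out of outputs labelled as bone disease. The effect is a possible undercount in those outputs only. No event disappears from the report, and neither the primary endpoint nor any formal inference is touched. The size cannot be stated, because event rates and coding are not given; the percentages above rest on an assumed 5% rate and an assumed capture share.

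The conclusion assumes that the SAP text is programmed literally. If the separate output specifications already group the fracture terms, only the SAP wording needs correcting. Priority is low: a cheap improvement.

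**What to change.** Before database lock:

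1. Define the bone special-interest group as adynamic bone disease plus all coded fracture terms in the MedDRA version finally chosen, and put the term list in the SAP.
2. Use this group in Tables 4.5.1.x, 4.5.2.x and Listing 7.6.
3. Keep adynamic bone disease and long bone fracture as separate rows, so that the present counts stay visible.
4. While editing, reconcile the description of Tables 4.5.2.1 and 4.5.2.2: SAP 11.1 presents them as summaries by system organ class and preferred term, whereas their titles in SAP 20 say sex and age group.

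The cost is one term list and a re-run of tables already planned. The downside is that some traumatic fractures will be counted; the listing lets a reader identify the terms concerned. Whether to add bone pain, bone deformity or osteopenia is a judgement for the sponsor and not part of this fix. If the sponsor prefers the two terms, the least it should do is give the reason and state the restriction in the titles. Widening the list after results are known would look data-driven.
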